### 2. PERMITTED TREATMENTS

As this is a routine care study, the management of the patient remains similar to standard practice. There are no prohibited treatments. The analgesic treatments taken by the patient will be noted in his or her observation book so that they can be taken into account in the analysis of the study.

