## **III DESIGN AND CONDUCT OF THE RESEARCH**

### **1. CLEAR STATEMENT OF PRIMARY AND, WHERE APPROPRIATE, SECONDARY EVALUATION CRITERIA**

#### **Primary endpoint:**

- Collection of VAS (burning sensation) after 1 hour of Qutenza patch application® .

In retrospective observations made at the CETD of the La Roche sur Yon Hospital, 70% of patients receiving a first Qutenza® patch reported more pain at 1 hour than at 30 minutes. For this reason, it was decided to evaluate the primary endpoint at 1 hour of application. Nevertheless, the pain at 30 minutes of application will be evaluated as a secondary endpoint.

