#### **Secondary evaluation criteria :**

- Collection of VAS (neuropathic pain) before insertion and VAS (neuropathic pain) at 2 months after insertion,
- Collection of the DN4 score before and at 2 months after implantation.

The DN4 questionnaire is used to estimate the probability of neuropathic pain. It is a score out of 10, if the patient's score is equal to or higher than 4/10 the test is positive.

Although the DN4 questionnaire is a questionnaire for the diagnosis of neuropathic pain, it is also used in the participating centres for patient follow-up as it is a simple, easy-to-use scale that has become standard in all CETD consultations.

This scale does not assess the intensity of pain, but its type and characteristics; equally important for patients in improving their quality of life. The DN4 can be compared before insertion and at follow-up. Pain intensity will be assessed via VAS.

- Collection of the EVA (burning sensation) at 30 minutes of exposure.
- Taking painkillers while applying the Qutenza® patch
- Collection of pain (burning and neuropathic pain) by EN within one week of insertion,
- Duration of burning sensation after application
- Cold application during the week following the installation,
- Taking painkillers in the week following insertion
- Measurement of the painful area before patching and 2 months after patching

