**Criteria assessed :**

The protocol consists of assessing the intensity of the burning sensation by means of a VAS at 30 minutes and 60 minutes of exposure.

It should be noted that the VAS evaluated before the Qutenza® patch, at 1 month and at 2 months after application concern the patient's neuropathic pain, whereas the VAS at 30 and 60 minutes are the pain related to the burning sensation.

Concomitant treatment(s) received by the patient prior to the application of Qutenza® and in particular those taken on the day of application of the Qutenza® patch will also be collected.

Patients will be reviewed in a medical consultation at 1 month and 2 months after insertion, according to standard practice. This last visit may be carried out at 2 months or at the latest at 3 months after insertion, depending on the organisation and availability of the department.

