**3. DESCRIPTION OF MEASURES TAKEN TO REDUCE AND AVOID BIAS**

Randomisation will be performed in an open-label fashion, according to 2 groups of patients: one group with cold application and another group without cold application on the Qutenza patch®. The randomisation will be stratified on the centre. It will be carried out according to a 1:1 ratio and will be performed in blocks. Patients will be randomised on the day of application.

Randomisation will be carried out via the Capture System software by connecting to the website: <https://nantes-lrsy.hugo-online.fr/CSOnline/>.

The connection will be carried out thanks to a login, a password and a study number, delivered by the data manager of the CHD Vendée of La Roche sur Yon.

The following information should be filled in:

- First initial of the name,
- First initial of the first name,
- Month and year of birth,
- Compliance with inclusion and non-inclusion criteria (yes/no), -      No opposition to the study collected (yes/no).

Randomisation will be carried out by the investigator after confirmation of the possibility of inclusion in the study and the collection of no objection.

The inclusion number will be assigned automatically during randomisation. An email confirmation will be sent to the person who performed the randomisation and to all the persons concerned at the centre.

The randomisation list will be drawn up by the study methodologist, [name], CHD Vendée before the start of the study. An explanatory guide to randomisation will be available online under Capture System.

The randomisation list will be protected by restricted access and accessible only by the study biostatistician.

4. DURATION OF PARTICIPATION FOR A SUBJECT IN THE RESEARCH AND A DESCRIPTION OF THE TIMING AND DURATION OF ALL TRIAL PERIODS, INCLUDING FOLLOW-UP WHERE APPLICABLE

The duration of a patient's participation will be 2 months from the day of the installation with a delay of up to 3 months depending on the availability and organisation of the service.

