#### **Main criterion**

The primary endpoint was the VAS collected 1 hour after the start of the procedure.

The mean VAS between the 2 groups (with or without cold application) will be estimated and compared using a linear mixed model taking into account the stratification criterion on the centre. The "cold application" criterion will be taken into account as a fixed effect and the centre as a random effect.

The main analysis will be "intention to treat". It may be supplemented by a "per-protocol" analysis. No intermediate analysis is planned.

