#### **Secondary criteria**

##### VAS (neuropathic pain) before and at 2 months after surgery

- The mean difference between the 2 groups (with or without cold application) will be estimated and compared using a linear mixed model taking into account the VAS score measured at baseline and the stratification criterion on the centre.

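### Does recording painkillers for use in the analysis mean that the 1-hour VAS will be adjusted for painkillers taken after randomisation?

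*Combined protocol and SAP*

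**What the plan says.** Section V.2 (Permitted treatments) prohibits nothing and states that analgesics "will be noted in his or her observation book so that they can be taken into account in the analysis of the study". It gives no method.

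Section VI.1 (Main criterion) compares the 1-hour VAS between arms in a linear mixed model in which the cold "criterion will be taken into account as a fixed effect and the centre as a random effect". The main analysis is by intention to treat, with a per-protocol analysis as an optional supplement. The 2-month VAS is analysed in a "linear mixed model taking into account the VAS score measured at baseline and the stratification criterion on the centre", and the DN4 score likewise.

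On timing, section III.3 says "Patients will be randomised on the day of application". Section III.1 lists two painkiller criteria among the secondary criteria: "Taking painkillers while applying the Qutenza® patch" and "Taking painkillers in the week following insertion". Section III.2 (Criteria assessed) adds that, of the concomitant treatments received before the patch, "in particular those taken on the day of application of the Qutenza® patch will also be collected".

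Section VI.1 opens with a descriptive analysis of all data, overall and by arm, with counts and proportions for qualitative variables. The methods that follow cover the VAS, the DN4, the 7-day pain score and cold use in the following week. They do not mention painkillers.

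**The concern.** Two things invite the worry.

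The first is wording. In VI.1, taking something into account means a term in the mixed model: cold, centre, baseline VAS, baseline DN4. Carried over to V.2, the same wording makes analgesics a covariate. The primary model does not list them, and nothing in section VI expressly rules them out.

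The second is timing. A painkiller taken during the patch hour comes after randomisation. Section I.2 describes application as often very painful and links it with analgesic use. Section III.1 reports that "70% of patients receiving a first Qutenza® patch reported more pain at 1 hour than at 30 minutes". If cold lowers pain, fewer patients in the cold arm will need a painkiller, and those who take one will tend to be those in most pain. Painkiller use is then partly a result of the arm and partly a marker of the outcome. Conditioning on it breaks the randomised comparison.

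At stake would be an understated cold effect. The trial is also open-label: if controls were given painkillers at a lower pain level, adjustment could make an inert intervention look harmful. And if V.2 were interpreted only after the data were seen, there would be two candidate primary results. A lesser complaint is that the painkiller criteria get no between-arm test or estimate, whereas cold use in the following week gets a Chi2 test.

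**Working it through.** **The plan's own figure.** Section VI.2 gives a difference of 2 points, SD 2.8, alpha 5%, power 90%, and 42 per group. Two-sided:

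n = 2 × [2.8 × (1.960 + 1.282) / 2]² = 41.19, rounded up to 42.

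The figure reproduces, and it belongs to an unadjusted comparison of two means. Painkillers play no part in it.

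**What adjustment would do.** From the documents: difference 2.0, SD 2.8. Assumed, because the documents give nothing: painkiller use without cold pC; correlation ρ between the pain that prompts a painkiller (at about 30 minutes) and the 1-hour VAS; relief τ within the hour; a cold effect of 2 points on the prompting pain; one threshold for both arms.

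- Thresholds in SD units: cC = z(1 − pC); cT = cC + 2/2.8.
- Use with cold: pT = 1 − Φ(cT).
- Within-arm slope at τ = 0: b0 = 2.8ρ[φ(cC) + φ(cT)] / [pC(1 − pC) + pT(1 − pT)].
- Adjusted difference, with the intention-to-treat difference held at 2.0: 2.0 − (b0 − τ)(pC − pT).

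For pC = 0.30 and ρ = 0.6: cC = 0.524, cT = 1.239, pT = 0.108, and b0 = 1.68 × (0.348 + 0.185) / (0.210 + 0.096) = 2.92. With pC − pT = 0.192:

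| τ | Adjusted difference | Power, 50 per arm |
|---|---|---|
| 0 | 1.44 | 77% |
| 1 | 1.63 | 86% |
| 2 | 1.82 | 93% |

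The unadjusted model has 94% power at τ = 0 (power by simulation, no centre variance). With pC from 10% to 50%, ρ from 0.4 to 0.8 and τ from 0 to 2, the adjusted difference runs from 1.03 to 2.04. At ρ = 0.2 and τ = 2 it is 2.20, so the distortion can vanish or reverse.

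**No cold effect, unequal thresholds.** Let 40% of controls and 20% of cold patients take a painkiller at equal pain, with ρ = 0.6 and τ = 0. Then b0 = 2.80, and the adjusted model shows cold worse by 2.80 × 0.20 = 0.56 points, with type I error of about 19%. Intention to treat stays at 5%.

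**The convention behind these figures.** Holding intention to treat at 2.0 for every τ means that the direct effect of cold must grow as painkillers work better. Fix the direct effect at 2 instead. Then:

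- intention to treat = 2 − τ(pC − pT)
- adjusted = 2 − b0(pC − pT)

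With τ = 2:

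| pC, ρ | Intention to treat (power) | Adjusted (power) |
|---|---|---|
| 0.30, 0.6 | 1.62 (88%) | 1.44 (77%) |
| 0.50, 0.4 | 1.48 (78%) | 1.52 (77%) |

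In the second row the two are practically equal. Both the contrast and its size depend on assumptions.

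**Does the plan call for the adjusted model?** Set the sections side by side.

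- V.2 concerns permitted treatments. It says why analgesics are recorded and that they can be considered. It names no endpoint, model or covariate.
- VI.1 (Main criterion) is the section that defines the primary model, and it names two terms. A fully stated model excludes what it does not list.
- The wording is not uniform across section VI. In VI.4, accounting for missing data means describing numbers and reasons by group, with no model term. The English is also visibly translated, so a stock phrase is thin evidence of a modelling commitment.
- V.2 can be carried out without touching the primary model, because the two painkiller criteria in III.1 are tabulated by arm under the opening paragraph of VI.1.

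**The painkiller criteria.** With 50 per arm and assumed rates of 30% and 20%, the 95% interval for the risk difference has half-width 1.96 × √(0.30 × 0.70/50 + 0.20 × 0.80/50) = 0.169, or 17 points. A reader can work this out from the planned by-arm proportions. Duration of burning and painful area also have no method in VI.1, so the omission is general to the minor secondary criteria.

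**The case for a change.** The strongest case for a change is that V.2 states an analytic purpose which section VI never carries out, in wording that VI.1 uses for model terms. An analyst who took V.2 at its word could add a harmful covariate, and could mix intake before randomisation (a legitimate covariate) with intake after it. Settling this in advance would cost a sentence or two, and once the data are seen the choice can no longer be shown to be independent of them. In an open-label trial with unrestricted analgesia, painkiller use by arm also helps the reader interpret the 1-hour VAS.

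Some of this stands. V.2 is vague, adjustment for patch-hour painkillers would usually be a mistake, and the arithmetic is right on its assumptions. A sentence confirming the VI.1 model would do no harm.

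But it would only repeat what VI.1 already determines. Departing from the stated primary model would be a deviation from the plan, whatever V.2 says. The mixing of intake before and after randomisation is not established: III.2 speaks of treatments before the patch, III.1 lists patch-hour painkillers as a separate criterion, and the annex on data collected is not in the available text. Painkiller use by arm will be reported under VI.1.

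**Conclusion.** No change is needed. V.2 leaves a detail open, and VI.1 fills it: the primary result is the intention-to-treat comparison with cold and centre only, so it compares cold plus usual care with usual care, whatever painkillers are taken. Followed as written, the plan avoids the bias described.

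If an analyst departed from it, the distortion could matter: 1.44 instead of 2.0 in the central assumed case, and 1.03 to 2.04 over the assumed range. Those figures rest on use rates, a correlation, a painkiller effect and a common threshold that the documents do not contain, and on holding the intention-to-treat difference at 2.0. With a fixed 2-point direct effect and a 2-point painkiller effect, the two models give 1.62 and 1.44, or nearly the same value (1.48 and 1.52), depending on the inputs. The sample size of 42 evaluable and 50 randomised per arm is unaffected.

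The missing between-arm estimate for painkiller use is a matter of reporting detail. The proportions by arm are already planned, and an interval of about 17 points either side would add little to them.

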## VI STATISTICS

### 1. DESCRIPTION OF THE PLANNED STATISTICAL METHODS, INCLUDING THE TIMING OF PLANNED INTERIM ANALYSES

A descriptive analysis will be performed for all patient data overall and by randomisation arm. Quantitative variables will be described by mean, standard deviation, median, quartiles, extreme values. Qualitative variables will be described by the number of patients and the proportions according to the defined modalities.

#### **Main criterion**

The primary endpoint was the VAS collected 1 hour after the start of the procedure.

The mean VAS between the 2 groups (with or without cold application) will be estimated and compared using a linear mixed model taking into account the stratification criterion on the centre. The "cold application" criterion will be taken into account as a fixed effect and the centre as a random effect.

The main analysis will be "intention to treat". It may be supplemented by a "per-protocol" analysis. No intermediate analysis is planned.

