### **Conduct of the study :**

This is a multicentre study on 5 different geographical sites (La Roche sur Yon, Montaigu, Challans, Nantes, Les Sables D'Olonne). It is planned to randomise 100 patients in total. In order to compensate for possible patients who would be included (signed non-objection) but could not be randomised, a maximum of **110 patients will be included**. Enrolment will be completed once the study has reached 100 randomised patients.

Approximately two months before the first Qutenza® patch is applied, the patient is seen in an information consultation by a doctor as part of their treatment at the CETD. On this occasion, a nurse will complete the consultation by presenting the DIDOCAP study and by proposing to the patient to participate.

The patient will go home with the information leaflet. The patient's non-objection can be collected on the day of this consultation or at the latest on the day of the first patch of Qutenza®. The non-objection will be collected and signed by the doctor and/or the nurse.

If the patient refuses, he/she will receive the most appropriate treatment for his/her situation (Qutenza patch® with or without the application of cold, at the discretion of the medical team and according to the patient's choice in accordance with the standard practice of the centres).

If the patient accepts, a randomisation will be performed on the day of the Qutenza patch® (via the e-CRF). The two randomisation groups are :

- **Patient receiving Qutenza® without cold application or**
- **Patient receiving Qutenza® combined with cold application**

At each consultation (2 months before inclusion, on the day of inclusion (patching), at 1 month and at 2 months after patching) the patient will be seen by both a doctor and a nurse.

**Doctor:** The doctor prescribes the Qutenza® patch, and carries out the tracing with the nurse on the day of application in the day hospital. He also prescribes painkillers for the week following the application if necessary.

The doctor sees the patient again at 1 and 2 months.

**Nurse:** The nurse greets the patient, assesses the pain, performs a global evaluation, gives information about adverse events related to the procedure, applies the patch according to the doctor's instructions following the Qutenza® patch use procedure.

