##### EVA (burning sensation) after 30 minutes

- The mean VAS between the 2 groups (with or without cold application) will be estimated and compared using a linear mixed model taking into account the stratification criterion on the centre.

The evolution of the pain at 30 minutes and 1 hour will be represented graphically.

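### Cheap improvement, not an error: the 1-hour and 30-minute burning-VAS models could also adjust for the pre-patch neuropathic-pain VAS

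*Combined protocol and SAP*

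**What the plan says.** Section VI.1, Main criterion, compares mean 1-hour VAS between arms with a linear mixed model. The cold-application "criterion will be taken into account as a fixed effect and the centre as a random effect"; no other term is named. The 30-minute burning VAS is compared with a "linear mixed model taking into account the stratification criterion on the centre", again with no patient-level covariate.

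The 2-month neuropathic-pain VAS is handled differently: its model is described as "taking into account the VAS score measured at baseline and the stratification criterion on the centre". That baseline is a listed measurement in section III.1: "Collection of VAS (neuropathic pain) before insertion". Section III.2, Criteria assessed, separates the two kinds of pain: the scores before the patch and at 1 and 2 months are for neuropathic pain, whereas "the VAS at 30 and 60 minutes are the pain related to the burning sensation".

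On timing, section III.2 says of the day's procedure: "The nurse greets the patient, assesses the pain, performs a global evaluation". Section III.3 says: "Patients will be randomised on the day of application", open-label. The list there headed "The following information should be filled in" covers initials, month and year of birth, eligibility and non-opposition, with no pain score. Section III.6 refers the data collected to Annex A, which is not in the text available for this review.

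**The concern.** The primary model uses no information about the individual patient other than arm and centre, although a same-patient pain rating is taken before the patch and the plan already uses it elsewhere. If patients who report more neuropathic pain also tend to report more burning, leaving that score out gives a wider confidence interval than necessary for the main comparison and for the 30-minute one.

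Only precision is at stake. Randomisation makes the planned comparison unbiased with or without the covariate, and the one stratification factor, centre, is in the model. The question has to be settled early because the trial is open-label with a patient-reported endpoint: a covariate added after outcomes are seen would look like a choice made on the results.

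**Working it through.** **Inputs from the documents.** Difference 2 points (7 to 5), SD 2.8, alpha 5%, power 90%, 42 per group, 50 per arm randomised (section VI.2); 1:1 allocation (section III.3). The 2.8 is taken here as the SD of the 1-hour VAS.

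**Assumed.** R, the correlation of the pre-patch neuropathic VAS with burning VAS, is not in the documents; the range shown is 0 to 0.5. Centre effects are left out of the closed-form figures.

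**1. The plan's own figure.** n per group = 2 × [2.8 × (1.960 + 1.282) / 2]² = 41.2, rounded up to 42. This matches the plan with a two-sided test; a one-sided test would give 34. With the noncentral t distribution, power is 89.9% at 42 per arm and 94.3% at 50 per arm.

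**2. Planned model, 50 per arm.** SE = 2.8 × √(2/50) = 0.560 on 98 df. The 95% CI half-width is 1.984 × 0.560 = 1.111 points.

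**3. Model with one covariate.** SE = 2.8 × √(1 − R²) × √(2/50) × √(1 + 1/96) on 97 df. The last factor is the expected cost of chance imbalance in the covariate, 1 + 1/(N − 4) with N = 100.

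| R | SE ratio to planned | CI half-width | Power |
|---|---|---|---|
| planned model | 1 | 1.111 | 94.3% |
| 0 | 1.005 | 1.117 | 94.0% |
| 0.1 | 1.000 | 1.112 | 94.2% |
| 0.2 | 0.985 | 1.095 | 94.8% |
| 0.3 | 0.959 | 1.066 | 95.8% |
| 0.5 | 0.871 | 0.968 | 98.2% |

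Break-even is where (1 − R²)(1 + 1/96) = 1, so R = √(1/97) ≈ 0.10. The SE ratios do not depend on the SD; power and half-width do.

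**4. Missing covariate values.** This was simulated: REML mixed model with random centre, five sites of 40/10/25/12/13, blocks of 4, centre SD 0.5, 10% of covariate values missing at random, 2,000 trials per cell. All of these settings except the five sites are assumptions. With missing values filled by the overall mean, the SE ratio is 1.005, 0.987, 0.964 and 0.885 at R = 0, 0.2, 0.3 and 0.5. With those patients dropped, it is 1.061, 1.040, 1.012 and 0.919. Dropping patients therefore costs 6.1% at R = 0 and removes the gain at R = 0.3; filling keeps most of it.

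**5. Type I error.** In 3,000 null trials per setting, the rate with the covariate was 5.3%, 5.6% and 4.9% at R = 0, 0.3 and 0.5, against 5.3%, 5.4% and 5.0% for the planned model (Monte Carlo SE 0.4 points).

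**The case against.** **The gain is unproven and may be trivial.** Burning caused by the patch is a different pain from the neuropathic pain it treats, and no correlation is documented. At R = 0.2 to 0.3 the half-width shrinks by 0.02 to 0.05 points, which would hardly change a conclusion about a 2-point effect. This stands, and it is why the point is optional. The counterweight is that the worst case is a 0.5% larger SE.

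**The 2-month model is not a true precedent.** There the pre-patch VAS is the baseline of the model's own outcome. This also stands. A reader might infer that the plan contradicts itself by adjusting at 2 months and not at 1 hour; it does not. The closer parallel is the 7-day numerical score, which includes neuropathic pain and is also adjusted only for centre.

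**The trial might be underpowered without the covariate.** Section VI.2 attaches 2.8 to a decrease from an initial burn score, so a reader might infer a 1-hour SD as high as 3.6 and planned power of 78.5%. That needs equal SDs at both times and a correlation of 0.7: 2.8 / √(2 × 0.3) = 3.61. Neither figure is in the documents. Section I.2 describes burning as developing progressively, so the initial score may vary little, leaving the 1-hour SD near 2.8. On a 0 to 10 scale with mean 7, a beta distribution with SD 3.6 would be U-shaped (shape parameters 0.43 and 0.19). The argument is not relied on here.

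**The timing may already be settled.** A reader might infer that the plan fails to require the score before allocation. With Annex A unavailable, that cannot be established; it is a point to confirm.

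**Other covariates may be as useful.** Section V.2 says analgesics are noted for use in the analysis, and section III.2 collects treatments taken before the patch. Nothing here rules out a pre-randomisation covariate of that kind, provided it is fixed in advance.

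**Conclusion.** The point holds as an optional efficiency gain. The planned analysis is valid, and the sample size reproduces and stands without the covariate. If R exceeds about 0.1, the interval for the cold-application effect narrows: by 1.5% in SE at R = 0.2, 4.1% at R = 0.3 and 13% at R = 0.5. If R is zero, the cost is 0.5% in SE and about 0.2 points of power at the stated SD. Because planned power is already 94.3% at 50 per arm, precision is the main benefit.

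These figures rest on an assumed R and a linear relation; the power and half-widths also rest on 2.8 being the SD of the 1-hour VAS. No separate SD or effect is given for the 30-minute score, so only the SE ratios carry over to that model. Confidence that the change is worthwhile is moderate, because nothing in the documents shows where R lies.

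**What to change.** In section VI.1, before any outcome data are seen:

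- Specify both burning-VAS models (1 hour and 30 minutes) with arm and pre-patch neuropathic-pain VAS (linear) as fixed effects and centre as a random effect.
- Use the score recorded before the allocation is known. Confirm this against Annex A, or make the score a required field on the randomisation page, which would also prevent most missing values.
- Fill any missing covariate value with the overall baseline mean across both arms, so that all randomised patients stay in the intention-to-treat analysis.
- Report the arm-plus-centre model as a sensitivity analysis.
- Keep post-randomisation variables, such as analgesics taken during application, out of the primary model.

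The cost is a few lines of text, possibly one extra field, and one degree of freedom. No new measurement is needed. The sponsor should judge whether the edit is a substantial modification that must be notified under section IX.2.
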